2.2 Outcome of AEs

The outcome of the AE should be documented as:

- 1. Recovered / resolved
- 2. Recovering / resolving
- 3. Not recovered / not resolved
- 4. Recovered / resolved with sequelae

- 5. Fatal
- 6. Unknown

2.3 Action taken

The action taken by the Investigator or study staff should be documented as:

- 1. Drug withdrawn
- 2. Dose reduced
- 3. Dose increased
- 4. Dose not changed
- 5. Unknown
- 6. Not applicable

2.4 Severity of AE

Severity refers to the grading of adverse events to assess the severity of symptoms as evaluated by the investigator or as experienced by the subject. The severity grading is independent of seriousness; in other words, a severe event is not necessarily serious.

The investigator will make an assessment of severity (e.g. mild, moderate or severe) for each AE and SAE reported during the study in accordance with the Common Terminology Criteria for Adverse Events (CTCAE) criteria (version 4.03: June 14, 2010).

The severity of the AE will be assessed by the Investigator, based on their clinical judgement and documented as:

- 1. Mild No limitation to normal activities
- 2. Moderate Some limitation to normal activities
- 3. Severe Inability to carry out normal activities

3. ADVERSE EVENT FOLLOW UP

All adverse events will be followed:

• to resolution

or

• until an underlying condition has been diagnosed or

- until the patient's condition has stabilised or
- for a period of 28 days following the last administration of the study drug or the last study visit, whichever is soonest.

Any new or unresolved AEs noted at the last study visit will be followed up for a further 28

days unless they fulfil the above criteria.

All pregnancies will be followed up until birth and any birth defects will be reported as in the procedures for SAEs (see section 3 and 4).

If the subject becomes pregnant while participating in the study, the pregnancy will not be recorded as an SAE, but will be captured on a Pregnancy Report Form and followed through until delivery or elective/spontaneous termination.

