7.9.2 FVIII Inhibitors

Both a FVIII inhibitor screen and a quantitative FVIII Nijmegen-Bethesda inhibitor test will be performed at Addenbrooke's Hospital, UK. All inhibitor samples will be collected after a 3 day washout period, when it is anticipated that the pre-substitution FVIII level has reached a nadir¹².

FVIII inhibitor screening test

For the FVIII inhibitor screens, an APTT is performed on a 50/50 mix of a subject's plasma and normal pooled plasma, and compared with the APTT for the subject's plasma and that of normal pooled plasma. A positive inhibitor screen is defined as one that does not correct the APTT by > 50% of the difference between the subject's value and the normal pooled plasma value. To rule out the presence of a time-dependent inhibitor, 50/50 mixes of the subject's plasma and normal plasma are compared following incubation together or separately for 2 hours at 37°C. Time-dependent inhibition is defined as > 4 seconds' prolongation of the incubated mixture relative to the plasmas incubated separately.

FVIII Nijmegen-Bethesda inhibitor test

A Nijmegen-Bethesda assay will also be performed using the same sample as above. A result of ≥ 0.6 BU confirms that the subject has developed inhibitors to FVIII. If this occurs, the test will be repeated on a separate sample; if both tests are confirmed to be ≥ 0.6 BU this will be reported by

the Investigator as an SAE (see Appendix I). The Central Laboratory will notify both the Contract Research Organisation (CRO) and Sponsor immediately if any sample has a value of ≥ 0.6 BU, even if the repeat analysis has not been conducted.

If there is a discrepancy between the FVIII inhibitor screen and Nijmegen-Bethesda assay result, analyses will be repeated on reserve samples and, if necessary, additional samples from the subject, until an unequivocal result, or a reason for the discrepancy, is obtained.

If necessary, repeat FVIII inhibitor quantitative assays will be performed on reserve samples from earlier timepoints, in an attempt to identify the point at which an immune response was initiated. The subject's progress will be monitored closely and if any additional FVIII inhibitor samples are required, these should be taken in triplicate to allow repeat testing and assessment of possible 'transient' inhibitors.

If required, additional methodologies may be used to detect and quantitate inhibitors to FVIII. Any such methodologies will be described in detail in the clinical study report.

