9 SUBJECT WITHDRAWAL

Subjects may stop study treatment for any of the following reasons:

• Withdrawal of consent.

- Significant protocol deviation.
- Lost to follow-up.
- Incidental illness.
- Occurrence of adverse events (AEs) not compatible with the continuation of the subject's participation in the study, in the Investigator's opinion (*eg* anaphylactic or other severe/serious reaction to infusion, development of inhibitor).
- Investigator's request.
- Requirement for therapeutic intervention prohibited by the protocol *eg* FVIII containing product or antifibrinolytics agents (expect during surgery).
- Premature termination of the trial by BPL on account of an unacceptable risk-benefit ratio. If this occurs, BPL or BPL's representatives will notify the regulatory authorities, ethics committees and Investigators of the reason for premature study termination, within 15 days from the study being halted.
- Subject/guardian is unco-operative and non-compliant with respect to provisions of the protocol.
- Trial stopped by BPL as 10 evaluable subjects have 100 EDs with Optivate[®].
 NB:this may mean that the last two subjects enrolled into the study may receive a shorter treatment period.

The clinical Investigator may also remove a subject if, in his/her opinion, it is in the best interests of the subject.

Subjects are free to withdraw from the study at any time without providing reason(s) for withdrawal and without prejudice to further treatment. The reason(s) for withdrawal will be documented where possible, particularly where withdrawal is a consequence of an adverse event. The subject's primary care physician (where applicable) will be informed of the reason for withdrawal.

Data collected up until a subject's withdrawal from the study, including data for screen failures, will be retained on the clinical database and used in the analysis and clinical study report.

Subjects withdrawing from the study will be requested to complete the same final assessments as subjects completing the study according to the protocol, particularly safety assessments (see Section 7.4). If there is a medical reason for withdrawal, the subject will remain under the supervision of the Investigator until in satisfactory health or the subject's condition has stabilised.

Reasonable efforts will be made to contact subjects who are lost to follow-up. These efforts must be documented in the subject's medical records.

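### Appendix I gives serious adverse events no follow-up rule of their own, so an unresolved SAE may stop being followed at diagnosis or at a 28-day limit that does not match Section 9 or the SAE reporting rule

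*Protocol*

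**What the plan says.** Appendix I Section 3 opens with "All adverse events will be followed" and then gives four alternatives. The first is resolution. The second is "until an underlying condition has been diagnosed or", the third "until the patient's condition has stabilised or", and the fourth "for a period of 28 days following the last administration of the study drug or the last study visit, whichever is soonest". An extension follows: "Any new or unresolved AEs noted at the last study visit will be followed up for a further 28", counted in days, with an exception at its end: "days unless they fulfil the above criteria". Pregnancies have their own longer rule in the same section (to birth). Serious events have none.

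Four other places bear on the same events:

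- **Section 9 (Subject Withdrawal).** If the reason for withdrawal is medical, "the subject will remain under the supervision of the Investigator until in satisfactory health" or until the condition is stable. The section names inhibitor development as an example of an adverse event that may lead to stopping.
- **Appendix I Section 4.** SAEs are reportable up to 28 days after the last dose. Those judged related remain reportable when they start later than that.
- **Section 7.9.2.** After a positive inhibitor result the subject is monitored closely. If further samples are needed, "these should be taken in triplicate to allow repeat testing and assessment of possible" transient inhibitors. No duration is given.
- **Sections 7.4.3 and 7.5.** The subject is discharged after V4. The one scheduled contact afterwards is a telephone call 28 days after the last infusion.

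**The concern.** The study asks about immunogenicity and tolerability in 10 evaluable subjects, so each serious case will be read individually, and its outcome is part of what can be learned from it. A rule that lets the record close while the event is open weakens that reading. The sections also give sites different instructions for the same event: one permits an exit at diagnosis or at a time limit, another recognises neither exit for a medical withdrawal, and a third calls for reports of events that begin after the limit has passed. The extension meant to protect events found at the last visit is worded so that the limit above it may cut it short.

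**Working it through.** **The plan's own timing.** Section 4.3 gives 4 weeks of screening, up to 52 weeks of treatment and a call 28 days after the last infusion: 4 + 52 + 28/7 = 60 weeks, as stated. The Appendix VI flow chart, with its 28-day month, puts V4 at 9 to 12 months and the safety call at 9 + 1 = 10 to 12 + 1 = 13 months, also as stated. The intended period after the last dose is therefore 28 days.

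**How the limit interacts with the extension.** Let g be the number of days from last dose to last visit, and count days from the last visit (day 0). The fourth alternative can be read in two ways:

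- Reading A: 28 days from the last dose or 28 days from the last visit, whichever ends first. Stop day = min(28 − g, 28).
- Reading B: 28 days from the last dose, or the last visit itself, whichever comes first. Stop day = min(28 − g, 0).

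The extension aims at day +28.

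| g (days) | Reading A stop day | Reading B stop day |
|---|---|---|
| 0 | +28 | 0 |
| 14 | +14 | 0 |
| 28 | 0 | 0 |
| 42 | −14 | −14 |

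For a completer, Section 7.4.2 gives the last bolus at V4, so g = 0. Reading A then keeps the full 28 days and agrees with the 60-week duration, the telephone call and the flow chart. Reading B would end follow-up at V4 and contradict the extension. Values of g above 0 are assumptions: the documents give no dose-to-visit gap for withdrawn subjects. The shortening also depends on the extension's exception including the time limit among its criteria.

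**Sections side by side.**

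1. Diagnosis exit: present in Appendix I Section 3, absent from Section 9. The 28-day exit: likewise. Stabilisation appears in both.
2. A related SAE starting on day d after the last dose, with d > 28, is reportable under Appendix I Section 4. Measured from the last dose, the Section 3 limit leaves 28 − d < 0 days for following it. Section 4 asks for a complete form and follow-up reports but sets no end-point.
3. An inhibitor first found at V4 comes from the pre-dose sample (Section 7.4.1). Confirmation needs a separate sample (Section 7.9.2) and a recovery assessment (Section 8.1.1). Neither can be done by telephone, and no section says how long such a case is followed.

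**Effect on planned outputs.** The adverse-event tables in SAP Section 10.2 do not summarise outcome, and SAP Section 9.1 summarises exposure days to positive status. No planned summary changes.

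**The case against.** The strongest reply is that this is loose wording with little consequence. Several parts of it stand.

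- A reader might infer that all follow-up ends at the earlier of diagnosis and 28 days. The text does not support that: resolution and stabilisation are also listed, and the soonest wording sits inside the fourth alternative, where it most naturally chooses between last dose and last visit.
- A reader might infer that the rule cancels its own extension. For completers under reading A it does not. Full cancellation under that reading needs a gap of at least 28 days, which no section describes.
- A reader might infer that an inhibitor case closes on the day it is confirmed. The exit refers to an underlying condition, most naturally the cause behind a symptom, whereas a confirmed inhibitor is the event itself. Sections 7.2.3, 7.7.2 and 7.9.2 allow more visits and further inhibitor testing with no time limit.
- A reader might infer that outcomes become unknown. Appendix I Section 2.2 has a separate code for events not recovered, and Appendix I Section 4 requires follow-up SAE reports. Details are left to a Safety Management Plan that is not among the documents.
- Section 9 speaks of clinical supervision, not data collection, and does not cover completers, so the mismatch is narrow.

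The reply does not remove the absence of a serious-event rule, the diagnosis exit for an open SAE, or the limit that expires before a late related SAE begins. Section 7.9.2 makes further sampling conditional and gives no duration, so it does not say when outcome collection ends.

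**Conclusion.** The point holds in a limited form. As written, an unresolved SAE may leave follow-up at diagnosis, or 28 days after the earlier of last dose and last visit. That does not match Section 9 for medical withdrawals or Appendix I Section 4 for late related SAEs. Under reading A the extension loses nothing at g = 0, is shortened by g days when g lies between 0 and 28, and is lost altogether at 28 or more, with g above 0 assumed throughout. Final outcomes, including that of an inhibitor first detected at V4, may go unrecorded; the documents do not support saying that they will be unknown.

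One subject is 1/12 = 8.3% to 1/10 = 10% of the set. That is the weight of a single case, not an estimate of how many would be affected. Nor do the documents show that serious events concentrate among subjects who stop early. No statistical figure or planned table changes; what improves is the completeness of the safety narrative.

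**What to change.** Amend Appendix I Section 3, as to outcome-data collection only:

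1. Reconcile it with Section 9, Section 7.9.2 and Appendix I Section 4.
2. Confine the diagnosis and 28-day exits to non-serious events.
3. For SAEs, including the automatically serious list in Appendix I Section 1.3, and for events leading to withdrawal, collect outcome to the end-point already stated in Section 9 and report status at database lock. That end-point includes stabilisation, so the reconciled text should say how it applies to an inhibitor monitored under Section 7.9.2.
4. Replace the soonest wording with the later of the two dates, and state that the last visit is a starting point for the 28 days. The stop day is then max(28 − g, 28) = +28 for every g of 0 or more.
5. State that the criteria named in the extension's exception exclude the time limit. Keep the exception itself: deleting it would require 28 more days of follow-up for events that have already resolved.

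The cost is a wording amendment, a few extra contacts for the small number of open serious events, and some outcomes updated close to database lock.

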4. REPORTING SERIOUS ADVERSE EVENTS

When an Adverse Event occurs which fulfils the definition of serious (see Section 1.3 for definition) the Investigator must:

Complete and sign the serious adverse event form and send it within 24 hours to the appropriate person as detailed in the Safety Management Plan.

Medical cover for urgent queries relating to adverse events will be provided on a 24 hours / 7 days a week basis by the following CRO Pharmacovigilance Department INC Contact:

Address: [name] Email: [contact] [contact] or to the dedicated fax number indicated on the SAE Fax Cover

Page

The Investigator is responsible for expedited reporting of all Serious Adverse Events immediately to BPL and/or the designated CRO (as stated in the Safety Management Plan)

CONFIDENTIAL

Page 66 of 100

except for those that the protocol or Investigator's Brochure identifies as not requiring immediate reporting. This reporting requirement covers any serious adverse events that develop at any point between the date when a subject provides informed consent and up to 28 days after the last administration of the investigational medicinal product. The Investigator is also responsible for reporting to BPL and/or the designated CRO (as stated in the Safety Management Plan) any serious adverse events with an onset date more than 28 days after the last administration of the product if he/she judges the serious adverse event to be possibly, probably or very likely/certainly related to the product.

The immediate report should contain the following as a minimum:

- 1. A suspected investigational medicinal product
- 2. Study subject number
- 3. Details of the serious adverse event
- 4. Classification of SAE
- 5. Causality of SAE (if available)

The immediate SAE form should be followed by a detailed, complete SAE form as soon as possible. The immediate report and follow-up reports shall identify subjects by unique code numbers assigned to the latter.

Adverse Events and/or laboratory abnormalities identified in the protocol as critical to the evaluation of safety must be reported to BPL and/or the designated CRO (as stated in the Safety Management Plan) by the Investigator according to the reporting requirements within the time periods specified in this protocol.

The investigator must not wait to receive additional information to document fully the event before notification of a SAE, though additional information may be requested. Where applicable, information from relevant laboratory results, hospital case records and autopsy reports should be obtained.

Instances of death, congenital abnormality or an event that is of such clinical concern as to influence the overall assessment of safety, if brought to the attention of the investigator at any time after cessation of IMP administration and linked by the investigator to this study should be reported to BPL or the designated CRO (as stated in the Safety Management Plan).

BPL and / or the designated CRO will promptly notify all relevant investigators and the regulatory authorities of findings that could adversely affect the safety of patients, affect the conduct of the study or alter the IEC/IRB approval/favorable opinion of the study. In addition, the sponsor (or designated CRO), will expedite the reporting to all concerned investigators, to the IECs/IRBs, where required, and to the regulatory authorities of all adverse events that are serious, unexpected, and in the opinion of the investigator, related to the IMP.

The investigator will comply with local requirements related to the reporting of SAEs, IND Safety Notification Letters, and other safety information related to the trial to their local IRB.

For reported deaths of a subject, the Investigator shall supply BPL and /or the designated CRO (as stated in the Safety Management Plan) and the Research Ethics Committee with any additional information requested.

Completing Serious Adverse Event Forms

Serious Adverse Event (SAE) forms must be completed in a timely manner and contain the following information:

- subject number, sex, date of birth, study centre, trial code,
- description of event (where possible a diagnosis should be made rather than just listing symptoms),
- study drug, indication for use, batch number, dose, route, date and time of last dose,
- date and time of adverse event,
- all concomitant medication (copy of concomitant medication page can be appended),
- causal relationship to study medication (as in Section 2.2),
- outcome (as in Section 2.3),
- action taken and treatment given (as in Section 2.4),
- severity (as in Section 2.5),
- classification of serious adverse event (as in Section 1.3),

The SAE form must be signed and dated by the person reporting the SAE. The final report must be signed and dated by the Principal Investigator from the site.

5. BPL'S RESPONSIBILITIES

BPL and/or the designated Contract Research Organisation (as stated in the Safety Management Plan) will be responsible for reporting all relevant safety information (including a listing of all SUSARs) to the competent authorities and to the Independent Ethics Committee (IEC) / Institutional Review Board (IRB) concerned. In the case of blinded studies the IEC / IRB and Competent Authority will be provided with an unblinded listing and in order not to bias the study the listing will be provided by an independent person. Safety reports will be issued in accordance with local relevant procedures (as a minimum on an annual basis).

BPL and/or the designated CRO (as stated in the Safety Management Plan) will inform the relevant competent authority (ies) in line with regulatory guidelines on adverse events occurring during the trial. The Investigator retains the right to inform the relevant competent authority(ies) if he/she so desires but must inform BPL and/or the designated CRO (as stated in the Safety Management Plan) so that duplicate reports to the competent authority(ies) can be highlighted.

BPL and/or the designated CRO (as stated in the Safety Management Plan) will inform all Investigators of all suspected unexpected serious adverse reactions occurring during the study or findings that could adversely affect the safety of subjects.

APPENDIX II - ADMINISTRATIVE REQUIREMENTS

ABBREVIATIONS AND DEFINITIONS

ARSAC	- Administration of Radioactive Substances Committee
BPL	- Bio Products Laboratory Limited
CA	- Competent Authority
CI	- Chief Investigator
COI	- Coordinating Investigator
CRA	- Clinical Research Associate
CRF	- Case Record Form
e-CRF	- Electronic Case Record Form
CV	- Curriculum Vitae
DQF	- Data Query Form
EU	- European Union
FDA	- Food and Drug Administration
GCP	- Good Clinical Practice
GMC	- General Medical Council
ICH	- International Conference on Harmonisation
ID	- Identification
IEC	- Independent Ethics Committee
IMP	- Investigational Medicinal Product
IRB	- Institutional Review Board
PI	- Principal Investigator
R&D	- Research and Development
SOP	- Standard Operating Procedure

- CA 'Competent Authority', synonymous with 'Regulatory Authority': the Government body that has the power to regulate. In the context of ICH GCP, the term 'Competent Authority' includes the authorities that review submitted clinical data and those that conduct inspections.
- CI 'Chief Investigator': in relation to a clinical trial conducted at a single trial site, the Investigator for that site. In relation to a clinical trial conducted at more than one trial site, the authorised health care professional, whether or not

he/she is an Investigator at any particular site, who takes primary responsibility for the conduct of the trial.

- COI 'Coordinating Investigator': an investigator assigned the responsibility for the coordination of investigators at different centres participating in a multicentre trial.
- PI 'Principal Investigator': a doctor or person following a profession for investigations because of the scientific background and the experience in subject care it requires. The Principal Investigator is responsible for the conduct of the trial at the trial site. If a trial is conducted by a team of individuals at a trial site, the Principal Investigator is the leader responsible for the team.
- IEC 'Independent Ethics Committee': a review board or a committee, institutional, regional, national or supranational, constituted of medical/scientific professionals and non-medical/non-scientific members, whose responsibility it is to ensure the protection of the rights, safety and well being of human subjects involved in a clinical trial and to provide public assurance of that protection, by, among other things, reviewing and approving / providing favourable opinion on, the trial protocol, the suitability of the Investigator(s), facilities and the methods and material to be used in obtaining and documenting informed consent of the trial subjects.
- IRB 'Institutional Review Board': an independent body constituted of medical, scientific and non-scientific members, whose responsibility is to ensure the protection of the rights, safety and well being of human subjects involved in a clinical trial by, among other things, reviewing, approving and providing continuing review of the trial protocol and amendments and of the methods and material to be used in obtaining and documenting informed consent of the trial subjects.
- IMP 'Investigational Medicinal Product': a pharmaceutical form of an active substance or placebo being tested or used as a reference in a clinical trial, including products already with a marketing authorisation but used or assembled in a way different from the authorised form, or when used for an

unauthorised indication, or when used to gain further information about the authorised form.

